#### **PCSA Listings**

A listing of individual data from patients with post-baseline PCSAs will be provided; values will be flagged when reaching the PCSA criteria.

### **14.8.4 Electrocardiogram**

ECG parameters (HR in bpm, QTc, QT, QRS and PR in msec) will be derived from the ECG obtained in hospital or during Visit days as per schedule of events. All parameters will be analyzed as raw data and absolute change from baseline. In addition, for the abnormalities analysis, PR and QRS will be also analyzed as percent change from baseline.

### **Baseline definition**

The values to be used as baselines will be the Day 1 predose assessment values. If any of the scheduled baseline tests are repeated for any subject, the last rechecked values will be considered as baselines, provided they were done before the IMP administration of the respective treatment phase, and in the same condition.

### **Abnormalities analyses**

For all parameters, analysis will be performed, using all post-baseline assessments done during the TEAE period, including all unplanned and rechecked values. Counts of patients with PCSAs will be presented by treatment, regardless of the baseline status.

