### 8.3 EXCLUSION CRITERIA

- E 01. History of Type 1 diabetes mellitus
- E 02. Appears unlikely or unable to participate in the required study procedures, as assessed by the study Investigator, study coordinator, or designee (ex: clinically-significant psychiatric, addictive, or neurological disease), or sectioned due to an official or court order
- E 03. Tachyarrhythmia with ventricular rate  $> 130$  bpm at screening, unless determined to be clinically stable by the investigator current admission for worsening heart failure primarily triggered by causes such as acute coronary syndrome, pulmonary embolism, cerebrovascular accident, heart valve disorders (such as severe aortic stenosis), as determined by the Investigator

- E 04. Clinically significant myocardial infarction (MI) within past 1 month as determined by Investigator and with objective evidence from ECG, and/or cardiac imaging and/or coronary angiography. Small isolated elevations in troponin that often accompany HF hospitalization are not an exclusion, nor are clinically significant MIs that have been re-vascularized without complications
- E 05. Patients who recently had or scheduled to have cardiac interventions may be eligible if:
- Stable 48 hours post procedure AND
  - Have diuretic treatment planned for the duration of treatment in this study
- E 06. Current use of or recent suspension of digoxin therapy with high levels of digoxin (level should be obtained and must be <1.2 ng/mL) at screening.
- E 07. History of heart or kidney transplant
- E 08. Diagnosis of hypertrophic obstructive cardiomyopathy
- E 09. End-stage HF defined as requiring left ventricular assist device insertion, intra-aortic balloon placement (IABP), or any type of mechanical support during the study period
- E 10. Pregnancy (demonstrated by serum pregnancy test at screening), breast-feeding, or inability or refusal to undergo pregnancy testing
- E 11. Use of any investigational drug(s) or prohibited therapy or sodium-glucose co-transporter 2 (SGLT2) inhibitor 5 half-lives prior to screening
- E 12. Patients with moderate or severe respiratory, hepatic, neurological, psychiatric, active malignant tumor or other major systemic disease (including any diseases with evidence of malabsorption), making implementation of the protocol and/or the interpretation of the study results difficult

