#### **Abnormalities analyses**

For parameters with laboratory ranges and/or abnormality criteria (PCSA), analysis will be performed using all post-baseline assessments done during the TEAE period, including all unplanned and rechecked values. Counts of patients with PCSAs according to baseline status will be presented by treatment. The same type of summary tables will be provided for out-of-normal laboratory range values.

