- for adults: Criteria for Potentially Significant Abnormalities – for Phase 2/3 studies (oncology excepted) - Version 3.0 - 21-MAY-2014
- for children: Criteria for Potentially Clinically Significant Abnormalities for Studies in Children - Version 3.0 - 21-MAY-2014

ECG Parameter	Adults	Children
PCSA criteria n/N1 (%)		
Heart rate		
Low, at least grade 1 (adults)	<50 bpm	
Low, at least grade 2 (adults)	<40 bpm	
Low, at least grade 3 (adults)	<30 bpm	

ECG Parameter	Adults	Children
PCSA criteria n/N1 (%)		
Low and decrease from baseline, all grades	<50 bpm and decrease from baseline ≥ 20 bpm	Birth/0 to 27 days old : ≤ 90 bpm and decrease from baseline ≥ 20 bpm 28 days/1 month to 23 months old: ≤ 80 bpm and decrease from baseline ≥ 20 bpm 24 months/2 years to <6 years old: ≤ 75 bpm and decrease from baseline ≥ 20 bpm 6 to <12 years old : ≤ 50 bpm and decrease from baseline ≥ 20 bpm 12 to 16/18 years old : ≤ 50 bpm and decrease from baseline ≥ 20 bpm
At least grade 1 (adults)	<50 bpm and decrease from baseline ≥ 20 bpm	
At least grade 2 (adults)	<40 bpm and decrease from baseline ≥ 20 bpm	
At least grade 3 (adults)	<30 bpm and decrease from baseline ≥ 20 bpm	
High, at least grade 1 (adults)	>90 bpm	
High, at least grade 2 (adults)	>100 bpm	
High, at least grade 3 (adults)	>120 bpm	
High and increase from baseline, all grades	>90 bpm and increase from baseline ≥ 20 bpm	Birth/0 to 27 days old : ≥ 190 bpm and increase from baseline ≥ 20 bpm 28 days/1 month to 23 months old: ≥ 175 bpm and increase from baseline ≥ 20 bpm 24 months/2 years to <6 years old: ≥ 140 bpm and increase from baseline ≥ 20 bpm 6 to <12 years old : ≥ 120 bpm and increase from baseline ≥ 20 bpm 12 to 16/18 years old : ≥ 120 bpm and increase from baseline ≥ 20 bpm
At least grade 1 (adults)	>90 bpm and increase from baseline ≥ 20 bpm	
At least grade 2 (adults)	>100 bpm and increase from baseline ≥ 20 bpm	
At least grade 3 (adults)	>120 bpm and increase from baseline ≥ 20 bpm	
PR		
High, all grades	>200 ms	Birth/0 to 27 days old : ≥ 120 ms 28 days/1 month to 23 months old: ≥ 140 ms 24 months/2 years to <6 years old: ≥ 160 ms 6 to <12 years old : ≥ 170 ms 12 to 16/18 years old : ≥ 180 ms
At least grade 1 (adults)	>200 ms	

ECG Parameter	Adults	Children
PCSA criteria n/N1 (%)		
At least grade 2 (adults)	>220 ms	
At least grade 3 (adults)	>240 ms	
High and increase from baseline (adults)		
At least grade 1	>200 ms and increase from baseline $\geq 25\%$	

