At least grade 2	>220 ms and increase from baseline $\geq 25\%$	
At least grade 3	>240 ms and increase from baseline $\geq 25\%$	
QRS		
High, all grades	>110 ms	Birth/0 to 27 days old : ≥ 85 ms 28 days/1 month to 23 months old: ≥ 85 ms 24 months/2 years to <6 years old: ≥ 95 ms 6 to <12 years old : ≥ 100 ms 12 to 16/18 years old : ≥ 110 ms
At least grade 1 (adults)	>110 ms	
At least grade 2 (adults)	>120 ms	
High and increase from baseline (adults)		
At least grade 1	>110 ms and increase from baseline $\geq 25\%$	
At least grade 2	>120 ms and increase from baseline $\geq 25\%$	
QTc Fridericia		
Increase from baseline, Grade 1	Increase from baseline [30-60] ms	All age classes: Increase from baseline (30-60] ms
Increase from baseline, Grade 2	Increase from baseline >60 ms	All age classes: Increase from baseline >60 ms

References:

- for adults: Criteria for Potentially Significant Abnormalities – for Phase 2/3 studies (oncology excepted) - Version 3.0 - 21-MAY-2014

- for children: Criteria for Potentially Clinically Significant Abnormalities for Studies in Children - Version 3.0 - 21-MAY-2014

Vital signs parameter	Adults	Children
PCSA criteria n/N1 (%)		
Systolic blood pressure supine		
Low and decrease from baseline	≤95 mmHg and decrease from baseline ≥20 mmHg	Birth/0 to 27 days old : ≤ 60 mmHg and decrease from baseline ≥20 mmHg 28 days/1 month to 23 months old: ≤ 70 mmHg and decrease from baseline ≥20 mmHg 24 months/2 years to <6 years old: ≤ 70 mmHg and decrease from baseline ≥20 mmHg 6 to <12 years old : ≤ 80 mmHg and decrease from baseline ≥20 mmHg 12 to 16/18 years old : ≤ 90 mmHg and decrease from baseline ≥20 mmHg
High and increase from baseline	≥160 mmHg and increase from baseline ≥20 mmHg	Birth/0 to 27 days old : ≥ 85 mmHg and increase from baseline ≥20 mmHg 28 days/1 month to 23 months old: ≥ 98 mmHg and increase from baseline ≥20 mmHg 24 months/2 years to <6 years old: ≥ 101 mmHg and increase from baseline ≥20 mmHg 6 to <12 years old : ≥ 108 mmHg and increase from baseline ≥20 mmHg 12 to 16/18 years old : ≥ 119 mmHg and increase from baseline ≥20 mmHg
Diastolic blood pressure supine		
Low and decrease from baseline	≤45 mmHg and decrease from baseline ≥10 mmHg	Birth/0 to <6 years old : ≤ 34 mmHg and decrease from baseline ≥10 mmHg 6 to <12 years old : ≤ 48 mmHg and decrease from baseline ≥10 mmHg 12 to 16/18 years old : ≤ 54 mmHg and decrease from baseline ≥10 mmHg

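### Eleven of the 24 graded ECG limits are absolute, but their by-arm counts are not split by Day 1 status, so stable pre-existing findings and small new crossings share one row

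*Protocol*

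**What the plan says.** **ECG.** Protocol 14.8.4 counts potentially clinically significant abnormalities (PCSAs) "using all post-baseline assessments done during the TEAE period, including all unplanned and rechecked values". It then says: "Counts of patients with PCSAs will be presented by treatment, regardless of the baseline status". SAP 2.7.4 has the same rule. Section 14.8.4 adds that "for the abnormalities analysis, PR and QRS will be also analyzed as percent change from baseline".

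**Limits.** SAP Appendix C gives two kinds of adult ECG limit:

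- Absolute: heart rate <50, <40, <30 and >90, >100, >120 bpm; PR >200, >220, >240 ms; QRS >110, >120 ms.
- Baseline-referenced: each of those grades again, with a required change. For heart rate the form is ">90 bpm and increase from baseline" of at least 20 bpm, and a fall of at least 20 bpm for the low limits. For QRS it is ">110 ms and increase from baseline" of at least 25%, and PR is treated the same way. QTcF has only change limits (30 to 60 ms; more than 60 ms).

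**Other safety data.** For laboratory values, protocol 14.8.2 states: "Counts of patients with PCSAs according to baseline status will be presented by treatment", and SAP 2.7.2 agrees. Vital signs (14.8.3, SAP 2.7.3) are not split by baseline, but every adult vital-sign limit in Appendix C also requires a change from baseline.

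**The concern.** ECG results belong to the primary safety endpoint. Under the rule above, a patient whose QRS is 150 ms on Day 1 and still 150 ms on Day 14 is counted in the >110 and >120 ms rows of the arm, just like a patient who developed the finding on treatment. ECG is the only domain in the plan that combines stand-alone absolute limits with no split by baseline: laboratory limits are split, and vital-sign limits all carry a change component. The documents give no reason for the difference.

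Two things are at stake in the by-arm table. A chance imbalance on Day 1 can look like a treatment difference in these rows, and a true difference in new onset is diluted.

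**Working it through.** No sample size, power or error rate in the documents depends on this rule, so there is no stated figure to reproduce. The check has three steps.

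**1. How many limits are affected (SAP Appendix C, adult graded limits)**

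| Parameter | Absolute | Change required |
|---|---|---|
| Heart rate, low | 3 | 3 |
| Heart rate, high | 3 | 3 |
| PR | 3 | 3 |
| QRS | 2 | 2 |
| QTcF | 0 | 2 |
| Total | 11 | 13 |

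11/24 = 46%. Counting the rows labelled as all grades as well gives 13 absolute and 15 change-based, again 46%. Adding to the 24 graded limits the two absolute QTc flags of SAP Appendix D, which are listing flags rather than Appendix C limits, gives 13 and 13.

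**2. Which new findings appear by arm only in an absolute row**

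These are new crossings whose change is too small for the paired row:

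- QRS 105 to 125 ms: 20/105 = +19%. Newly crosses both QRS grades; below 25%.
- PR 195 to 242 ms: 47/195 = +24%. Newly crosses all three PR grades; below 25%.
- Heart rate 85 to 104 bpm: +19 bpm. Newly crosses >90 and >100; below 20 bpm.

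A patient starting at PR 200 ms must reach 200 × 1.25 = 250 ms to enter the paired row.

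**3. How far an absolute row can be diluted**

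Let b be the share over the limit on Day 1, assumed to persist, and p the new-crossing rate among the rest.

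- Tabulated rate = b + (1 − b)p.
- Difference between arms = (1 − b)(p_active − p_placebo).
- Pre-existing share of the active count = b / [b + (1 − b)p_active].

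The 27 per arm (400 mg and placebo) come from the Total row of protocol Table 1. The documents give neither b nor p; p = 5% on placebo and 20% on active, and the range of b, are assumptions.

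| b | Placebo count | Active count | Difference (points) | Pre-existing share, active |
|---|---|---|---|---|
| 10% | 27 × 0.145 = 3.9 | 27 × 0.280 = 7.6 | 13.5 | 0.10/0.28 = 36% |
| 30% | 27 × 0.335 = 9.0 | 27 × 0.440 = 11.9 | 10.5 | 0.30/0.44 = 68% |
| 50% | 27 × 0.525 = 14.2 | 27 × 0.600 = 16.2 | 7.5 | 0.50/0.60 = 83% |

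With b = 0 the difference would be 15 points.

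With no drug effect, chance alone gives the between-arm difference in pre-existing cases a standard deviation of √(2 × 27 × b(1 − b)): √4.86 = 2.2 patients at b = 10%, √11.34 = 3.4 at 30% and √13.5 = 3.7 at 50%.

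**The case against.** The strongest reply is that the plan handles baseline for ECG by other means. Every absolute heart rate, PR and QRS grade has a partner that requires a change, and QTcF is change-only. Protocol 14.8.4 and SAP 2.7.4 summarise raw values and absolute change by treatment, so a Day 1 imbalance in means would be visible. SAP 2.7.4 lists each patient with a post-baseline PCSA with raw value and change, and SAP Appendix D flags the baseline value. Protocol 10.2.1 compares each trace with the screening trace and has new abnormalities rechecked. The safety review uses individual data as well as tables, which is feasible with about 64 patients. The rule also says openly that baseline is ignored, so nothing labels these counts as new onset, and no test of ECG counts is planned.

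All of that stands. It means that no information is lost and that the change-based rows are sound. It does not supply a by-arm count of new crossings below 25% or 20 bpm. A reader must assemble that from listings, although the frequency table is where arms are compared.

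Three stronger readings are tempting, and the documents do not support them:

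- *Most ECG limits are absolute.* Step 1 gives 46%, and 50% at most.
- *Any new QRS above 120 ms from a start of 96 to 120 ms, or new PR above 220 ms from 176 to 220 ms, escapes the paired row.* Those starting values (120/1.25 = 96; 220/1.25 = 176) are where a crossing can be smaller than 25%, not where it must be. QRS 100 to 130 ms is +30% and is caught.
- *E 03 shows that fast Day 1 rates are common.* It admits a ventricular rate above 130 bpm "unless determined to be clinically stable by the investigator", but it concerns screening, up to 21 days before Day 1, and gives no frequency.

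**Conclusion.** The point holds in a limited form. In 11 of 24 graded ECG limits, a stable abnormality already present on Day 1 is counted as a post-baseline PCSA, and small new crossings are mixed with it in the only by-arm row where they appear. The 13 change-based limits are unaffected.

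The size is unknown, because the documents give no baseline ECG rates. The factor (1 − b) follows from persistence alone; the 36% to 83% pre-existing share rests also on the assumed onset rates and on b between 10% and 50%. A reader might infer that the ECG counts mainly reflect who was abnormal on Day 1, or that new findings are hidden. The first would need a high b that nothing in the documents establishes: at b = 10% it is 36% of the active count. The second is contradicted by the paired rows and the listings. This is a cheap improvement to a primary safety summary, not a flaw that invalidates it.

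**What to change.** In protocol 14.8.4 and SAP 2.7.4, present the absolute heart rate, PR and QRS rows by treatment and by Day 1 status against the same limit: patients not meeting it (or with no Day 1 value) in one row, patients already meeting it in another, each with its own denominator. This follows the practice already planned for laboratory PCSAs. Leave the change-based ECG rows and the vital-sign criteria as they are.

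The cost is a wording change and one extra split in an existing table, with no new data. The downside is smaller denominators: at b = 30% about 27 × 0.7 = 18.9 patients per arm would be in the row not meeting the limit on Day 1, and at b = 50% about 13.5.

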### **Descriptive statistics and plots**

ECG parameters (raw data and absolute change from baseline) will be summarized in descriptive statistics by treatment and scheduled time of measurement.

Additionally, graphs over time will be presented plotting mean +/- SD by treatment.

## **14.9 ANALYSIS OF PHARMACOKINETIC DATA FROM COHORT 1 AND 2**

See also [Section 10.3](#).

### **14.9.1 Pharmacokinetic parameters**

No formal analysis of PK parameters will be performed. Single concentration-time-points will be subject to descriptive statistical analysis.

## **14.10 INTERIM ANALYSIS**

Except DMC safety review planned after cohort 1 and cohort 2, there are no planned interim analysis.

## **15 ETHICAL AND REGULATORY CONSIDERATIONS**

### **15.1 ETHICAL AND REGULATORY STANDARDS**

This clinical trial will be conducted by the Sponsor, the Investigator, delegated Investigator staff and Sub-investigator, in accordance with consensus ethics principles derived from international ethics guidelines, including the Declaration of Helsinki on Ethical Principles for Medical Research Involving Human Subjects, adopted by the General Assembly of the World Medical Association (1996), and the ICH guidelines for Good Clinical Practice (GCP), all applicable laws, rules and regulations.

This clinical trial will be recorded in a free, publicly accessible, internet-based registry, no later than 21 days after the first subject/patient enrollment, in compliance with applicable regulatory requirements and with Sanofi public disclosure commitments.

### **15.2 INFORMED CONSENT**

The Investigator (according to applicable regulatory requirements), or a person designated by the Investigator and under the Investigator's responsibility, should fully inform the patient of all pertinent aspects of the clinical trial including the written information giving approval/favorable opinion by the ethics committee (IRB/IEC). All participants should be informed to the fullest extent possible about the study, in language and terms they are able to understand.

Prior to a patient's participation in the clinical trial, the written informed consent form should be signed, name filled in, and personally dated by the patient and by the person who conducted the informed consent discussion. A copy of the signed and dated written informed consent form will be provided to the subject.

The informed consent form used by the Investigator for obtaining the patient's informed consent must be reviewed and approved by the Sponsor prior to submission to the appropriate ethics committee (IRB/IEC) for approval/favorable opinion.

The written informed consent form and any other written information to be provided to patient should be revised whenever important new information becomes available that may be relevant to the subject's consent. Any revised written informed consent form, and written information should receive the IRB/IEC's approval/favorable opinion in advance of use. The patient should be informed in a timely manner if new information becomes available that may be relevant to the patient's willingness to continue participation in the trial. The communication of this information should be documented. In case of study suspension due to safety concerns, study patients will be informed of this study suspension and the reason for it. Once it is confirmed that it is safe for the study to continue, study patients will be asked to confirm their agreement to continue the study.

### **15.3 HEALTH AUTHORITIES AND INSTITUTIONAL REVIEW BOARD/INDEPENDENT ETHICS COMMITTEE (IRB/IEC)**

As required by local regulation, the Investigator or the Sponsor must submit this clinical trial protocol to the Health Authorities (Competent Regulatory Authority) and the appropriate IRB/IEC, and is required to forward to the respective other party a copy of the written and dated approval/favorable opinion signed by the chairman with IRB/IEC composition.

The clinical trial (study number, clinical trial protocol title and version number), the documents reviewed (clinical trial protocol, informed consent form, Investigator's Brochure with any addenda, Investigator's curriculum vitae, etc.) and the date of the review should be clearly stated on the written IRB/IEC approval/favorable opinion.

IMP will not be released at the study site and the Investigator will not start the study before the written and dated approval/favorable opinion is received by the Investigator and the Sponsor.

During the clinical trial, any amendment or modification to the clinical trial protocol should be submitted to the Health Authorities (Competent Regulatory Authority), as required by local regulation, in addition to the IRB/IEC before implementation, unless the change is necessary to eliminate an immediate hazard to the patients, in which case the Health Authorities (Competent Regulatory Authority) and the IRB/IEC should be informed as soon as possible. They should also be informed of any event likely to affect the safety of patients or the continued conduct of the clinical trial, in particular any change in safety. All updates to the Investigator's Brochure will be sent to the IRB/IEC and to Health Authorities (Competent Regulatory Authority), as required by local regulation.

A progress report is sent to the IRB/IEC at least annually and a summary of the trial's outcome at the end of the clinical trial.

## **16 STUDY MONITORING**

### **16.1 RESPONSIBILITIES OF THE INVESTIGATOR(S)**

The Investigator is required to ensure compliance with all procedures required by the clinical trial protocol and with all study procedures provided by the Sponsor (including security rules). The Investigator agrees to provide reliable data and all information requested by the clinical trial protocol (with the help of the case report form, discrepancy resolution form, or other appropriate instrument) in an accurate and legible manner according to the instructions provided and to ensure direct access to source documents to Sponsor representatives.

If any circuit includes transfer of data, particular attention should be paid to the confidentiality of the patient's data to be transferred.

The Investigator may appoint such other individuals as he/she may deem appropriate as Sub-investigators to assist in the conduct of the clinical trial in accordance with the clinical trial protocol. All Sub-investigators shall be appointed and listed in a timely manner. The Sub-investigators will be supervised by and work under the responsibility of the Investigator. The Investigator will provide them with a copy of the clinical trial protocol and all necessary information.

### **16.2 RESPONSIBILITIES OF THE SPONSOR**

The Sponsor of this clinical trial is responsible to regulatory authorities for taking all reasonable steps to ensure the proper conduct of the clinical trial as regards ethics, clinical trial protocol compliance, and integrity and validity of the data recorded on the case report forms. Thus, the main duty of the monitoring team is to help the Investigator and the Sponsor maintain a high level of ethical, scientific, technical and regulatory quality in all aspects of the clinical trial.

At regular intervals during the clinical trial, the site will be contacted, through monitoring visits, letters or telephone calls, by a representative of the monitoring team to review study progress, Investigator and patient compliance with clinical trial protocol requirements, and any emergent problems. These monitoring visits will include but not be limited to review of the following aspects: patient informed consent, patient recruitment and follow-up, SAE documentation and reporting, AESI documentation and reporting, AE documentation, IMP allocation, patient compliance with the IMP regimen, IMP accountability, concomitant therapy use, and quality of data.

